addition to sponsor-based debriefings, the semi-structured interviews we will conduct with the interventionists during the Aim 2 and Aim 3 studies will also provide a linkage for them to the overall study and will, hopefully, provide them with a sense of ownership in the developing system.

*Caregivers.* It will only be family caregivers who will be part of the clinical trial component of this study (in Aims 2 and 3). Recruitment into the studies will be through referral from the sponsoring organizations. Each organization will recruit caregivers to take part in Savvy programs provided by interventionists trained in the system we are developing. We will provide organizations with materials they can use to announce Savvy and the studies; we will encourage the organizations to insert these materials into their own standard informational templates (i.e., standard logo and graphics). For caregivers willing to do so, their contact information will be provided to the Emory study team. We will arrange a phone or video call with each during which we will explain the study (Aim 2 or Aim 3 – a caregiver will not be able to take part in both), explain eligibility criteria, and seek informed consent (verbally) for participation. We do not anticipate attrition to be a problem in the Aim 2 study; research contact, following consent, will occur over a very brief period of time. All who consent to the Aim 2 study will take part immediately in a Savvy program and in an on-line survey and (for some) in-person interview conducted by phone or video right after the program. Prolonged retention will be more of a challenge in the Aim 3 study. Those taking part will enter a Savvy program either immediately or after a delay based on scheduling at the individual agencies. For those taking part immediately a series of 3 phone or video interviews will bracket their Savvy participation (at baseline then at 3 and 6 months following baseline. For those with a delayed start, we will conduct 4 interviews (upon sign up, immediately prior to the start of the program and then 3 and 6 months after program completion). To foster engagement with the project, we will prepare and distribute to participants a monthly project newsletter,

featuring tips on exercise and healthy eating and profiles of the study team. We will also send birthday and seasonal holiday cards, as appropriate.

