### *Participant Discontinuation/Withdrawal from the Study*

Participants are free to withdraw from participation in the study at any time upon request. The reason for participant discontinuation or withdrawal from the study will be recorded on the study REDCap. Subjects who receive all or part of the study intervention will not be replaced.

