## **Data Management**

Data will be entered at the time of each interview directly into the dedicated project tablet computer and saved on Emory's secure REDCap platform. All data entry screens are set up in REDCap and, where possible, include data delimiters (i.e., skip patterns, valid range limits) to ensure correctness and minimize missing data. Data will be exported weekly and analyzed for data cleaning and verification. Upon completion of each cohort data-gathering point, all data will be merged for scale computation, aggregation, and analysis. In preliminary analyses, descriptive statistics and frequency distributions will be examined to identify outliers and ensure integrity of merged files. For all multi-item scales, internal consistency will be examined using Cronbach's alpha and associated statistics (e.g., item-total correlations, alpha if item deleted).

Preliminary analyses will examine baseline differences among completers and non-completers and by study arm (immediate/delayed) as a randomization check using 2-group comparison tests (t-tests and non-parametric equivalent tests for continuous variables (normally or non-normally distributed) and Chi-Square tests for categorical variables). The association of predisposing factors (demographics, CG history, relationship and care recipient status at baseline) at baseline data with changes in outcomes over time will be examined to identify significant covariates. Where significant associations with baseline measures are detected, these potential confounders will be controlled for in subsequent analyses using covariate model adjustments.

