## **10. Plans for analysis**

Multi-level mixed effects models (MLM) with random (participant) and fixed (cohort) effects will be employed to test for linear (and non-linear) trajectories of change for the Intervention group versus waitlist

group focusing on the group-by-time effect. To address the primary effect of the Savvy intervention, the Immediate group will be compared to the waitlist delay group, using the first 2 time points (0m-2m) to test for differences between the 2 groups' changes post intervention. Additionally, the combined Savvy intervention effects will be assessed using a paired t-test for the combined immediate group's first 2 time points (0m-2m) with the waitlist delay group's 2 time points before and after beginning Savvy (4m-6m). If there are significant differences between the 2 groups at the time point immediately prior to receipt of the intervention, these "baseline" effects will be included and adjusted for a final analysis of covariance (ANCOVA) model for these change scores. Given that the immediate group will have 3 post-intervention measurements (2m-4m-6m), MLM longitudinal models will also be employed to assess the overall time effects plus planned post hoc comparisons for both the immediate intervention effect and the longer term and sustained effects. Sidak Type-I error rate adjustment (which has higher power than Bonferroni) will be applied for the multiple pairwise time point comparisons. The proposed study design also has the advantage of capturing "baseline" time points for the delay group (0m-2m-4m) which will provide an excellent opportunity to evaluate what if any potential "placebo" effects there may be from being enrolled in this type of study. These initial data captured at 0m-2m-4m for the delay group will also be used to evaluate any potential decline occurring during this time period. All model assumptions will be tested; grand mean centering used to help combat multi-collinearity between variables; and standard diagnostic tests and influence statistics used to test the distributions of the residuals. MLM models utilize all available data for all participants at each time point and have the advantage of adjusting for the missing data over time, where repeated measures ANOVAs do not. Further covariate predictors of missingness (mainly due to attrition) over time will be included to additionally adjust for these confounders SPSS v.24 will be used for all analyses at the 5% significance level.

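### The mixed model corrects the 0m-2m primary contrast only for dropout that measured data explain, no planned analysis probes the rest, and the combined effect is tested on complete pairs

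*Combined protocol and SAP*

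**What the plan says.** Section 10 sets out the main analysis: "Multi-level mixed effects models (MLM) with random (participant) and fixed (cohort) effects will be employed", with interest in the group-by-time effect. The primary comparison of immediate and wait-list caregivers is made "using the first 2 time points (0m-2m) to test for differences" between the arms' changes, so it has one post-baseline visit.

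On missing data, Section 10 says that mixed models use all available data and "have the advantage of adjusting for the missing data over time, where repeated measures ANOVAs do not". It adds: "Further covariate predictors of missingness (mainly due to attrition) over time will be included to additionally adjust for these confounders". Section 9 (Data Management) compares completers with non-completers on baseline variables and adjusts for baseline factors associated with change.

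The combined effect pools the immediate arm's 0m-2m pair with the wait-list arm's 4m-6m pair in a paired t-test. An ANCOVA on change scores follows if the groups differ just before receiving the program.

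On attrition, the Recruitment section says "Prolonged retention will be more of a challenge in the Aim 3 study". The withdrawal section says "The reason for participant discontinuation or withdrawal from the study will be recorded on the study REDCap". No planned analysis uses those reasons. No dropout rate, missing-at-random assumption or sensitivity analysis for missing scores appears anywhere.

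**The concern.** With one post-baseline visit, a caregiver who has no 2m interview contributes a baseline score and covariates to the primary contrast and nothing else. The likelihood then treats that caregiver as having changed like same-arm stayers with the same baseline and covariates. This is a real correction when those variables explain who is missing. It is an untested assumption when missingness also depends on the unseen 2m score, and the plan does not separate the two cases.

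The trial is an open wait-list comparison, so reasons for leaving can differ by arm. Section 10 later treats improved caregiver outcomes as a demonstration that system-trained interventionists can deliver Savvy faithfully. A bias in the contrast would feed into that reading.

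The combined analysis has a simpler problem. Having faulted repeated measures ANOVA on missing data, the same section uses a test that discards anyone lacking either visit of the pair.

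**Working it through.** The plan states no power, effect size, SD or dropout rate, so there is no figure of its own to reproduce. All inputs below are assumptions except the visits and the model.

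**Primary contrast**

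Inputs: 0m and 2m only, with a random participant effect (Section 10). Assumed: 60 per arm (N=120 is stated, the allocation ratio is not), 0m-2m correlation rho = 0.6, and a stayers' benefit of 0.40 SD.

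1. The 2m value implied for a caregiver missing at 2m is: same-arm stayers' 2m mean + rho × (own baseline − stayers' baseline mean). Planned covariates enter in the same way.
2. Let d be the share missing at 2m, and k the missing caregivers' shortfall beyond what step 1 predicts, for the immediate (I) and wait-list (W) arms. Then overstatement = dI·kI − dW·kW.
3. Suppose immediate-arm leavers gain nothing (kI = 0.40) and wait-list leavers do not differ from stayers (kW = 0). The model reports 0.40, and the effect of offering Savvy is 0.40 × (1 − d):
   - d = 10%: true 0.36; 0.04/0.36 = 11%
   - d = 20%: true 0.32; 0.08/0.32 = 25%
   - d = 30%: true 0.28; 0.12/0.28 = 43%

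   The ratio is d/(1 − d), so it does not depend on the assumed 0.40.
4. Suppose instead that leavers in both arms fall 0.4 SD short. Overstatement is 0.4 × (dI − dW):
   - 20% immediate / 20% wait-list: 0.00
   - 20% / 10%: +0.04
   - 30% / 10%: +0.08
   - 10% / 20%: −0.04 (understated)

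Simulation with the random-intercept likelihood model (60 per arm, 1,000 runs) agrees. Benefits are in SD:

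| Dropout (immediate/wait-list) | True | Completers | Mixed model |
|---|---|---|---|
| Immediate arm related to baseline, 20%/5% | 0.40 | 0.32 | 0.40 |
| Immediate leavers gain nothing, 20%/20% | 0.32 | 0.40 | 0.40 |
| Shortfall 0.4 in both arms, 20%/20% | 0.40 | 0.40 | 0.40 |
| Shortfall 0.4 in both arms, 20%/10% | 0.36 | 0.40 | 0.40 |
| Shortfall 0.4 in both arms, 10%/20% | 0.44 | 0.40 | 0.40 |

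Row one shows the model doing what Section 10 says. In rows two, four and five it does no better than completers.

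**Combined pre-post effect**

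Assumed: SD 1 at each visit, correlation 0.6, true change −0.30, 30% missing the second visit in the worse-baseline half and 10% in the better half.

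1. Each half's mean baseline is ±√(2/π) = ±0.798.
2. Stayers are 0.5 × 0.7 = 0.35 (worse half) and 0.5 × 0.9 = 0.45 (better half) of the total, 0.80 in all. Their mean baseline is 0.798 × (0.35 − 0.45)/0.80 = −0.10.
3. Expected change given baseline is −0.30 + (0.6 − 1) × baseline. Complete pairs therefore give −0.30 + (−0.4)(−0.10) = −0.26.
4. The likelihood estimate, which keeps the baseline of those who left, gives −0.30. Simulation returns the same two values.

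**Does a 2m score exist?**

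Section 5 (Study Design) and the Recruitment section place follow-up at 3 and 6 months. The delayed arm's only earlier interviews are at sign-up and just before the program. Field Methods and Section 10 use 2, 4 and 6 months. On the first schedule the primary contrast has no 2m wait-list value.

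**The case against.** **The plan does more than fit a mixed model.** It adds covariates that predict missingness and compares completers with non-completers at baseline. This stands: dropout explained by measured variables is handled. Neither step reaches dropout that depends on the unseen 2m score. The promise to test all model assumptions does not help, because observed data cannot test missing-at-random.

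**Leaving the program is not the same as missing the interview.** University staff interview by phone or video, apart from the sessions. They pursue missed contacts for four weeks, and each data collection brings a $25 card. Caregivers who stop attending but are interviewed enter the model with their real scores. The retention worry concerns prolonged follow-up, not 2m in particular. All of this stands, and it limits the point to missing interviews.

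**Importance.** This is a Stage I study, and its Aim 3 test is mainly about training interventionists. Fidelity evidence is read before caregiver outcomes, and the paired t-test is additional to the primary contrast. This also stands and keeps the point moderate.

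**Stronger readings that the documents do not support.** A reader might infer that every dropout is credited with the stayers' average benefit. The implied value in fact varies with own baseline and covariates. A reader might also infer that the effect is overstated whenever leavers do worse. The shortfall must be unexplained and larger, weighted by dropout share, in the immediate arm.

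Finally, a reader might infer a badly inflated false-positive rate. With zero effect of offering Savvy, 30% missing and a 0.5 SD shortfall, simulated rejection reaches about 0.23. That requires immediate-arm leavers alone to end 0.5 SD worse than comparable wait-list caregivers, while stayers gain 0.5 × 0.3/0.7 = 0.21 SD to offset them. If 0.5 SD is the gap from stayers, rejection is about 0.135. If both arms share the shortfall, it is near the nominal 5%. Nothing in the documents points to the extreme case.

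**Conclusion.** The concern holds in a limited form. Section 10's claim is right for dropout explained by baseline, arm, cohort and the planned covariates. Beyond that, the two-visit primary contrast rests on an unstated assumption that no planned analysis probes.

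The direction of bias is conditional on the arms' unexplained losses, and its size cannot be taken from the documents. The range of 11% to 43% rests on assumed 10% to 30% missing, no gain in immediate-arm leavers, and wait-list leavers no different from stayers.

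The complete-pair analysis is the firmer part, since it conflicts with the section's own reasoning whatever the dropout rate. The cost of 0.04 SD on a true 0.30 is illustrative and applies to the paired t-test. The change-score ANCOVA shares the loss of caregivers, although adjusting for the pre-program score may recover part of the bias.

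**What to change.** First reconcile the interview schedules in Section 5, Recruitment, Field Methods and Section 10. The primary contrast and step 2 below both need a wait-list 2m score. Then:

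1. Take the combined pre-to-post contrast from the mixed model, using all available visits, instead of the paired t-test or change-score ANCOVA.
2. Keep the mixed model as the primary analysis and report 2m missingness by arm. Add one sensitivity analysis that shifts the missing 2m scores separately in each arm over a range fixed in advance, and report the shifts at which the result loses significance.

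Shifting both arms is preferable to imputing immediate-arm leavers from the wait-list distribution alone. That imputation assumes no benefit but cannot represent harm. In the extreme case above it would still show about 0.7 × 0.21 = 0.15 SD when the truth is zero.

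The cost is SAP wording and a little extra programming, with no new data. The downside is a supporting estimate that may be less favourable than the main one.

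### No covariate-by-time term is named: covariates chosen for predicting change, and predictors of dropout, leave the 0m-2m group-by-time test unchanged in complete data if entered as main effects

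*Combined protocol and SAP*

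**What the plan says.** Section 10 (Plans for analysis) sets out the model: "Multi-level mixed effects models (MLM) with random (participant) and fixed (cohort) effects will be employed", "focusing on the group-by-time effect". The primary comparison of the immediate and wait-list groups is made "using the first 2 time points (0m-2m) to test for differences between the 2 groups' changes post intervention".

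Covariates reach this model by two routes.

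- **Section 9, Data Management.** The association of baseline factors "with changes in outcomes over time will be examined to identify significant covariates". Where associations are found, "these potential confounders will be controlled for in subsequent analyses using covariate model adjustments".
- **Section 10.** "Further covariate predictors of missingness (mainly due to attrition) over time will be included to additionally adjust for these confounders".

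Neither passage gives the form of the terms, and no covariate-by-time term appears anywhere. One secondary analysis differs. If the groups differ just before receiving the program, the combined comparison is "adjusted for a final analysis of covariance (ANCOVA) model for these change scores", and there a covariate acts on change directly.

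**The concern.** The selection rule and the tested effect both concern change, but an ordinary covariate acts on level. A baseline factor entered as a main effect shifts the 0m and 2m scores equally and drops out of their difference. If the plan is carried out that way, the report would describe a covariate-adjusted primary result in which chance imbalance on the chosen factors is uncorrected and no precision is gained. Under dropout, the step meant to deal with attrition would do only part of its work. Retention matters here: the Recruitment section expects it to be harder in the Aim 3 study.

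**Working it through.** **Inputs.** The model and contrast are those of Section 10. N=120 is from Section 4, Aim 3. The significance level is from Section 10 ("SPSS v.24 will be used for all analyses at the 5% significance level"). The documents give no allocation ratio, effect size, SD, power or dropout rate, so there is no planned figure to reproduce. Assumed: 60 per arm, residual SD 1, within-person correlation 0.6 given the covariate, covariate slope on change 0.3 or 0.5 SD, and dropout from 0 to about 33%.

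**Step 1: algebra.** Let G be group, t be 0 or 1, and X a baseline covariate.

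Y(t) = a + bG + ct + dGt + hX + u + e(t)

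Change = Y(1) − Y(0) = c + dG + e(1) − e(0)

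Both hX and the participant effect u cancel. With complete data the estimate of d is the raw difference in mean change, with or without X, and its standard error depends only on within-person variation. If X moves change by k per unit, an imbalance in X adds k × (difference in mean X) to the estimate. Only a term kXt removes it.

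**Step 2: fits to complete simulated data** (random-intercept REML, two visits; estimate and SE of group-by-time).

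| Dataset | No covariate | Main effect | Covariate-by-time |
|---|---|---|---|
| A | 0.290 (0.183) | 0.290 (0.183) | 0.081 (0.163) |
| B | 0.3490 (0.2299) | 0.3490 (0.2287) | 0.2161 (0.2322) |
| C | 0.0435 (0.190) | 0.0435 (0.190) | 0.0606 (0.169) |
| D | 0.0944 (0.1448) | 0.0944 (0.1448) | not fitted |

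The estimate is identical in every case. The SE is identical as long as the estimated participant variance is above zero. At zero, between- and within-person variation are pooled and the SE can move slightly; I take that to be the reason for the small difference in B. A and B were built with an unbalanced covariate, so the size of their shift illustrates the mechanism and is not an expected value.

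**Step 3: precision.** The variance of change given X is 2 × (1 − 0.6) = 0.8. If X is not modelled on change it is 0.8 + k². SE = √(variance × 2/60).

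- k = 0.5: √(1.05/30) = 0.187 against √(0.8/30) = 0.163, about 13% smaller. Simulated SD: 0.184 to 0.162 (12%), or 0.196 to 0.175 (11%) if X also predicts level.
- k = 0.3: √(0.89/30) = 0.172 against 0.163, about 5% smaller. Simulated with 22-23% missing: 0.186 to 0.179-0.180, about 4%.

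**Step 4: dropout, no true effect.** Bias in the group-by-time estimate, in residual SD units. Rows with slope 0.5, and the level-only row, rest on 400 runs each; the opposite-direction and one-arm rows with slope 0.3 on 2,000; the last row on 1,500.

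| X predicts | Dropout on X | Missing | None | Main effect | By time | Removed by main effect |
|---|---|---|---|---|---|---|
| Change (0.5) | Opposite by arm, log-odds 0.5 | 11% | −0.050 | −0.039 | −0.003 | 22% |
| Change (0.5) | Opposite, 1.0 | 33% | −0.282 | −0.240 | −0.002 | 15% |
| Level and change (0.5) | Opposite, 1.0 | 13.5% | −0.154 | −0.090 | 0.000 | 42% |
| Level and change (0.5) | Opposite, 1.0 | 24% | −0.274 | −0.172 | −0.005 | 37% |
| Level and change (0.5) | Opposite, 1.0 | 33% | −0.375 | −0.242 | −0.005 | 35% |
| Change (0.3) | Opposite | about 22% | −0.105 | −0.090 | −0.008 | 14% |
| Change (0.3) | One arm only | not recorded | −0.044 | −0.036 | 0.003 | 18% |
| Level only | Opposite | 33% | −0.116 | −0.010 | −0.011 | 91% |
| Change (0.3) | Same in both arms | 22-23% | at most 0.007 | at most 0.007 | at most 0.007 | little to remove |

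The last column is (none − main effect)/none; for example (0.375 − 0.242)/0.375 = 35%.

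Rejection at nominal 5% (none / main effect / by time) was 42% / 22% / 7% in the fifth row and 9.3% / 8.4% / 5.8% in the sixth. A separate run of the one-arm case gave 5.3% / 4.9% / 5.0%. With the same dropout relation in both arms it was 4.7-5.4% throughout.

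**The case against.** The strongest reply is that the plan never says main effects only. That is correct: it is silent. Section 10 also plans grand-mean centring, a step often tied to product terms, and the sentence on missingness carries citation 124 while the reference list ends at 111, so the intended method cannot be seen. This weakens the main-effects reading but does not displace it. Section 10 names the group-by-time interaction when it wants one and names none for covariates. The wording admits both an inert and an effective version.

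A reader might infer that main-effect covariates cannot adjust at all. That holds only without dropout. The missingness predictors are chosen for predicting dropout, not change, and where such a variable predicts level only, a main effect is enough.

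A reader might also infer a serious bias in the trial. The documents do not support that. Under randomisation with complete data the unadjusted contrast is unbiased over repeated trials. Material bias needs a covariate that predicts change together with dropout that depends on it differently by arm, and the documents give no sign of such a pattern.

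Nor does the covariate screening itself inflate error: outcome-based selection from 10-40 candidates gave 4.9-5.6% type I error. The change-score ANCOVA is a genuine exception, but it is conditional and belongs to the combined analysis. Finally, this is a Stage I project in which caregiver outcomes are preliminary efficacy, which limits the consequence.

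**Conclusion.** The point holds as an unstated model term that matters for the primary test. On the ordinary reading, the adjustment in Sections 9 and 10 has no effect on the 0m-2m group-by-time contrast when data are complete. That follows from algebra and needs no assumed effect size (for the SE, only a participant variance estimated above zero). The loss is uncorrected chance imbalance and a precision gain of roughly 4-12% in SD, for slopes of 0.3-0.5 SD on change and a within-person correlation of 0.6.

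The dropout figures are conditional. Main effects removed about 15-42% of the bias where a covariate drove change and dropout differed by arm, and the interaction brought it to within about 0.01 SD of zero. The slopes and dropout patterns are assumptions, since the documents give none.

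**What to change.** In Section 10, state that each adjustment covariate and each predictor of missingness enters the group-by-time model with its covariate-by-visit interaction. Alternatively, analyse the 2-month score with the baseline score and these covariates in the model. Point the Section 9 sentence on covariate adjustment to that statement.

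No new data are needed. The cost is one extra parameter per single-term covariate in the two-visit contrast, and more in the longer models if visit is categorical. If a covariate turns out to predict level only, the unneeded interaction loses a little precision: in the level-only simulation the SD rose from 0.186 to 0.194, about 4%. Fixing the covariate list in advance is optional and is not needed to correct this fault.
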